8.5 Study Halting Rules

This study may be temporarily suspended or prematurely terminated if there is sufficient reasonable cause. Written notification, documenting the reason for study suspension or termination, will be provided by the suspending or terminating party to all site investigators, the NIH/NHLBI, DSMB, and IRB. If the study is prematurely terminated or suspended, the PI will promptly inform the IRB and will provide the reason(s) for the termination or suspension.

Circumstances that may warrant termination or suspension include, but are not limited to:

- Determination of unexpected, significant, or unacceptable risk to participants
- Demonstration of efficacy that would warrant stopping
- Insufficient compliance to protocol requirements
- Data that are not sufficiently complete and/or evaluable
- Determination of futility

Study may resume once concerns about safety, protocol compliance, data quality are addressed and satisfy the sponsor, IRB, and/or DSMB. All participant data that was collected prior to study termination will be analyzed and continue to be handled/stored per this protocol.

Subsequent review of serious, unexpected, and related AEs by the DSMB and/or IRB may also result in suspension of the study.

8.6 Safety Oversight

Independent safety oversight will be provided by The UW ICTR Data Monitoring Committee (DMC). It is an independent team supported in its mission of safety and compliance by experienced ICTR staff to provide administrative assistance, experienced members representing a diversity of backgrounds (clinicians, biostatisticians, bioethicist), skills, and knowledge, and the use of the Research Electronic Data Capture (REDCap) tool, which provides data management functionality by allowing the development of eCRFs and surveys to support data capture. In providing oversight for the conduct of this study, the ICTR DMC will meet annually (every 12 months) during the 5-year study with opportunities to meet face-to-face or via phone and web depending on each individual's availability. The number of individuals will be determined by the UW ICTR. Additional meetings may be scheduled as determined by the DMC or as requested by the PI. The DMC members will review protocol-specific reports created by statisticians that serve a non-voting member role on the DMC using data pulled from REDCap. These standard reports will include an overview of study objectives, a review of actual and projected accrual rates, an evaluation of patient demographics for balance of randomization, and a summary of the number and seriousness of adverse events. An interim analysis of study results may be performed and source documents may be reviewed to allow the DMC to independently judge whether the overall integrity and conduct of the protocol remain acceptable based on data provided and reported by the Principal Investigator. The DMC will make recommendations to the Principal Investigator that could include actions of continuation, modification, suspension, or termination.

Data will be summarized and provided directly to the DSMB through the REDCap clinical trial software used for data collection during the study. The DSMB will keep minutes of its meetings, and the PIs and all study staff will receive verbal and written summaries of their reviews and recommendations.

See the DSMB charter in the Appendix

8.7 Unblinding Procedure

Although unlikely in this study, unblinding will be done in emergent medical circumstances. All efforts will be made to maintain blinding except in the case of urgent medical necessity. If a subject needs to be unblinded, the study site must document who broke the blind and the reason, and report the event to a member of the trial's executive leadership team (principal investigator, site investigator, and senior biostatistician) within 24 hours, who will instruct the data coordinating center to unblind.

9 Study Monitoring, Auditing, and Inspecting

9.1 Medical Monitoring

9.1.1 Study Monitoring Plan

Clinical site monitoring is conducted to ensure that the rights and well-being of human subjects are protected, that the reported trial data are accurate, complete, and verifiable, and that the conduct of the trial is in compliance with the currently approved protocol/amendment(s) and with applicable regulatory requirement(s).

- The PI and site PI will conduct monitoring, including on-site and centralized (via REDCap), initially weekly for the early/initial enrollment procedures, and then monthly. The monitoring will be comprehensive (100% data verification) via REDCap with random review of health coach calls. Monitoring reports will be available for the DSMB.
- Each clinical site will also perform internal quality management of study conduct, data collection, documentation, and completion as directed by ICTR/WINHR. An individualized quality management plan will be developed to describe a site's quality management.

See appendix for the auditing tool.

9.2 Protocol Deviations

A protocol deviation is any noncompliance with the clinical trial protocol or MOP requirements. The noncompliance may be either on the part of the participant, the investigator, or the study site staff. As a result of deviations, corrective actions are to be developed by the site and implemented promptly.

These will be reported per the HS IRB requirements (see appendix – reporting timeline). All deviations must be addressed in study source documents, reported to the NIH Program Official, DSMB, and IRB. Protocol deviations will be sent to the local IRB per their guidelines. The PI, site PI, and study staff are responsible for knowing and adhering to the IRB requirements.

9.2.1 Internal Data and Safety Monitoring Board

The Data Safety and Monitoring Plan (DSMP) for this research comprises research conducted at all sites for this proposal. All investigators and site principal investigators must agree to comply with the procedures outlined in this DSMP. This DSMP does not reduce any investigator's obligation to comply with the requirements of the Institutional Review Board (IRB).

All research activities conform to the NIH definition of a clinical trial. The UW ICTR Data Monitoring Committee (DMC) is an independent team supported in its mission of safety and compliance by experienced ICTR staff to provide

administrative assistance, experienced members representing a diversity of backgrounds (clinicians, biostatisticians, bioethicist), skills, and knowledge, and the use of the Research Electronic Data Capture (REDCap) tool, which provides data management functionality by allowing the development of eCRFs and surveys to support data capture. In providing oversight for the conduct of this study, the ICTR DMC will meet annually (every 12 months) during the 5-year study with opportunities to meet face-to-face or via phone and web depending on each individual's availability. The number of individuals will be determined by the UW ICTR. Additional meetings may be scheduled as determined by the DMC or as requested by the PI. The DMC members will review protocol-specific reports created by statisticians that serve a non-voting member role on the DMC using data pulled from REDCap. These standard reports will include an overview of study objectives, a review of actual and projected accrual rates, an evaluation of patient demographics for balance of randomization, and a summary of the number and seriousness of adverse events. An interim analysis of study results may be performed and source documents may be reviewed to allow the DMC to independently judge whether the overall integrity and conduct of the protocol remain acceptable based on data provided and reported by the Principal Investigator. The DMC will make recommendations to the Principal Investigator that could include actions of continuation, modification, suspension, or termination.

Data will be summarized and provided directly to the DSMB through the REDCap clinical trial software used for data collection during the study. The DSMB will keep minutes of its meetings, and the PIs and all study staff will receive verbal and written summaries of their reviews and recommendations.

See the DSMB charter in the Appendix section of the protocol.

9.3 Auditing and Inspecting

The investigator will permit study-related monitoring, audits, and inspections by the IRB (or their representatives), and/or the NIH of all study related documents (e.g., source documents, regulatory documents, data collection instruments, study data etc.). The investigator will ensure the capability for inspections of applicable study-related facilities (e.g., pharmacy, diagnostic laboratory, etc.).

9.4 Subject Compliance Monitoring

The study team will assess and track subject compliance through previously published methods.¹⁹¹ This will include:

- Intervention arm: Assessing the frequency that patients answer and complete health coach calls
- Intervention arm: Reviewing home blood pressure monitor directly during follow-up research visits and assessing the presence/absence of home reading availability during health coach calls
- Usual care and intervention arms: Frequency upon returning for study visits, completing phone surveys

After at least 3 call attempts, each 1-week apart, and 1 mailed letter attempt, if the participant does not return for the 6-month research study visit they will be withdrawn from the study and analyzed as intention to treat.

10 Ethical Considerations

This study is to be conducted according to NIH and Institutional research policies and procedures.

This protocol and any amendments will be submitted to a properly constituted independent Institutional Review Board (IRB), in agreement with local legal prescriptions, for formal approval of the study conduct. The decision of the IRB concerning the conduct of the study will be made in writing to the investigator and a copy of this decision will be provided to the sponsor before commencement of this study. The investigator should provide a list of IRB members and their affiliate to the sponsor.

All subjects for this study will be provided a consent form describing this study and providing sufficient information for subjects to make an informed decision about their participation in this study. See Appendix for a copy of the Subject Informed Consent Form. This consent form will be submitted with the protocol for review and approval by the IRB for the study. The formal consent of a subject, using the IRB-approved consent form, must be obtained before that subject undergoes any study procedure. The consent form must be signed by the subject and the investigator-designated research professional obtaining the consent.

11 Study Finances

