ClinicalTrials.gov number	ClinicalTrials.gov Identifier: NCT03158051
Phase	not applicable
Methodology	Randomized controlled Trial
Study Duration	5 years
Study Center(s)	Two Healthcare Systems - UW Health (Madison, WI) - Aurora Health Care (Milwaukee, WI)
Objectives	
Aim 1. To evaluate the effect of MyHEART (home blood pressure monitor distribution and health coaching) on clinical outcomes, the change in systolic and diastolic blood pressure (primary) and hypertension control (secondary) after 6 and 12 months, compared to usual clinical care. We hypothesize that MyHEART will significantly decrease systolic and diastolic blood pressures (clinic and 24-hour ambulatory) in young adults, compared to usual clinical care.
 
Aim 2. To evaluate the effect of MyHEART on hypertension self-management behavior (behavioral outcomes) at 6 and 12 months, compared to usual clinical care. We hypothesize that MyHEART will increase the frequency of home blood pressure monitoring and lifestyle modifications (increased physical activity, decreased sodium intake).
 
Aim 3. To examine whether MyHEART's effects on self-management behavior are mediated through variables of perceived competence, autonomy, motivation, and activation (mediation outcomes). Based on our pilot study and theoretical framework, we hypothesize that MyHEART's effects will be mediated through perceived competence, autonomy, internal motivation, and patient activation.

Number of Subjects	N=340
Diagnosis	uncontrolled hypertension
Main Inclusion Criteria	18-39 years with a diagnosis of "elevated blood-pressure reading, without diagnosis of hypertension" or a hypertension diagnosis, uncontrolled blood pressure ($\geq 140/90$ mmHg), and medically homed at one of the included clinical sites
Main Exclusion Criteria	Any of the following diagnoses: chronic kidney disease, congestive heart failure, sickle cell anemia, cystic fibrosis, stroke, myocardial infarction, coronary artery revascularization, or prior/planned organ transplant; inability to provide informed consent or read or communicate in English; residence at skilled nursing or correctional facility; prescription of warfarin, novel oral anticoagulant, planned chemotherapy, planned radiation therapy, plan to move out of area in next 6 months; pregnant or plan to become pregnant in next year; illegal drug use other than marijuana in past 30 days; syncope in past 12 months

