Study Product, Dose, Route, Regimen	Health coach face-to-face visits, with follow-up telephone calls, self-management support, and primary care provider feedback
FDA status of product	not applicable

Duration of administration	6-month intervention; 6-month maintenance evaluation (12-month total follow-up)
Reference therapy	Usual Clinical Care
Statistical Methodology	The primary comparisons for the co-primary outcomes of systolic and diastolic blood pressure change from baseline to 6 months will be done using analysis of covariance with MyHEART and baseline blood pressure as independent covariates. The primary comparisons for the secondary outcome of hypertension control will be based on Fisher's exact tests. Mediation analysis will be performed for Aim 3.

Schematic of Study Design

Figure: Eligibility, Enrollment, Randomization, Follow-up and Analysis

Contents

Study Summary.....	6
1 Key Roles.....	12
2 Background and Introduction.....	12
2.1 Background and Rationale.....	13
2.1.1 Development of MyHEART.....	13
2.2 Hypothesis.....	14
2.3 Study Agent.....	14
2.4 Summary of Clinical Data.....	15
2.5 Potential Risk and Benefits to Subjects.....	16
2.5.1 Known Potential Risks	16
2.5.2 Alternative to Study Participation	17
2.5.3 Protection Against Risks	17
2.5.4 Adverse Event Reporting	19
2.5.5 Potential Benefits to the Subjects	20
2.5.6 Risk Minimization	20
3 Study Design and Endpoints.....	21
3.1 General Design	21
3.1.1 Primary Study Endpoints.....	22
3.1.2 Secondary Study Endpoints.....	22
3.1.3 Primary Safety Endpoints.....	22
4 Study Subjects – Enrollment and Withdrawal.....	22
4.1 Subject Population	22
4.2 Inclusion Criteria.....	23
4.3 Exclusion Criteria	23
4.4 Subject Screening for Recruitment	24
4.4.1 Subject Identification	24
4.4.2 Recruitment and Retention Strategies	24
4.5 Vulnerable Populations	25
4.5.1 Subject Capacity	25
4.5.2 Subject/Representative Comprehension	25
4.6 Informed Consent.....	26
4.6.1 Process of Consent.....	26
4.6.2 Consent Form.....	26
4.6.3 HIPAA.....	26
4.6.4 Revoking Consent.....	27
4.6.5 Costs to the Subject	27
4.6.6 Payment for Participation	27
4.7 Early Withdrawal of Subjects	27

4.7.1	Premature termination of study	27
4.7.2	When and How to Withdraw Subjects.....	28
4.7.3	Data Collection and Follow-up for Withdrawn Subjects.....	28
5	Study Procedures	28
5.1	Prior and Concomitant Therapy	28
5.2	Randomization and Blinding of Intervention	28
5.3	Established Standard of Care	29
5.4	Study Visits.....	29

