3.1.1 Primary Study Endpoints

The co-primary clinical outcome is a significant, clinically important change in systolic and diastolic blood pressure at 6 and 12 months.^{21,36} The 6-month outcome assesses the end of the 6-month MyHEART intervention.⁴³ The 12-month outcome (*i.e.*, 6 months post-intervention)⁵⁸ assesses maintenance of blood pressure and sustainability of behavior change after study completion. In contrast to the baseline assessment, follow-up questionnaires and physiologic measurements will be conducted, obtained, and documented during the first visit of the 6- and 12-month visits to decrease missing data.

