6.1 Sample Size Determination

For Aim 1, approximately 930 individuals will be screened to get to a total of 340 enrolled participants (170 participants per randomized arm). This is designed under the assumption that there will be a further 15% dropout rate at the 6-month mark following randomization, to result in an effective sample size of 264.¹⁸⁴ In Nidich et al.,¹⁸⁵ the 3-month transcendental meditation program showed a mean difference of 6.3 and 4.0 in systolic and diastolic blood pressure change with a standard deviation of 13.6 and 9.7, respectively, as compared to a case of usual control among young adults at hypertension risk. With an effective sample size of 264, there is power of 0.94 and 0.87 for systolic and diastolic blood pressure, respectively, each at a two-tailed 0.025 test for an overall significance level of 0.05. For Aim 2, the effective sample size of 264 subjects will provide 90% power to detect a difference in the population mean difference from baseline to 6 months between treatment groups of about 0.4 standard deviations of the differences (moderate effect size). Aim 3 is an exploratory aim.

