6.2 Statistical Methods

See Appendix for the full Statistical Analysis Plan (SAP)

Statistical Analysis Plan Overview:

Data will be analyzed by intent to treat. Missing data will be imputed using multiple imputations.

For Aim 1, the comparisons for the primary outcomes of systolic and diastolic blood pressure change from baseline to 6 months will be done using analysis of covariance. The primary comparisons for the secondary outcome of hypertension control at 6 months will be based on Fisher's exact tests. Sequential hypothesis testing will also be performed. The 12-month analysis will focus on *maintenance* of behavior change, to assess whether significant differences seen between baseline and 6 months are retained. We will also assess the differential effectiveness of the intervention across subgroups by developing exploratory regression models.

For Aim 2, behavioral outcomes will be analyzed in a similar manner as with the clinical outcomes in Aim 1 depending on whether they are continuous or categorical. Analyses (t-tests or Wilcoxon tests and ANCOVA for continuous variables; Fisher's exact test for the categorical variable) will be performed for differences from baseline to 6 months between treatment groups. Linear or generalized linear mixed-effects regression models will be fit to describe longitudinal behavioral measurements over time.

For Aim 3, analyses will examine hypothesized mediators of the MyHEART intervention (for example, autonomy support, internal motivation, perceived competence, and patient activation). We will estimate mediation effects in multilevel models¹⁸⁶⁻¹⁹⁰ where mediation is assessed by fitting two models. Standard errors and 95% confidence intervals for the mediation effect and percent-mediated estimates will be calculated. This analysis will be pivotal to guide future replication and dissemination of MyHEART.

6.3 Planned Interim Analysis:

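### Participants who have not returned for the 6-month visit after repeated contact are withdrawn from the whole study, so no 12-month blood pressure is sought from them

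*Combined protocol and SAP*

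**What the plan says.** Section 9.4 sets the condition, "After at least 3 call attempts, each 1-week apart, and 1 mailed letter attempt", and then the consequence: "if the participant does not return for the 6-month research study visit they will be withdrawn from the study and analyzed as intention to treat". The withdrawal is from the study, not only from coaching, and it applies to both arms.

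The 12-month assessment is part of the stated purpose of the trial:

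- Aim 1 (Study Summary and 2.2) covers blood pressure change and "hypertension control (secondary) after 6 and 12 months, compared to usual clinical care".
- Section 3.1.1 words the co-primary outcome as "change in systolic and diastolic blood pressure at 6 and 12 months" and says the 12-month outcome "assesses maintenance of blood pressure and sustainability of behavior change after study completion".
- Section 6.2 plans a 12-month analysis "to assess whether significant differences seen between baseline and 6 months are retained".

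Section 4.7.3, which deals with follow-up of withdrawn subjects, gives an intention-to-treat label, multiple imputation and missing-data sensitivity analyses. It describes no further contact or measurement. Section 6.1 assumes a "15% dropout rate at the 6-month mark following randomization".

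**The concern.** Not returning at month 6 is a missed assessment. It is not a withdrawal of consent (4.6.4), and it is not one of the ineligibility or pregnancy grounds in 4.7.2 and 8.4.4. Section 9.4 nonetheless treats it as the end of participation, so every participant withdrawn under it also lacks a 12-month research blood pressure.

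The maintenance question then depends on how well imputation represents people who were never measured after baseline. Non-return could plausibly be related to arm, because only the intervention arm has a course of 12 coaching calls to disengage from. It could also be related to blood pressure. The observed data cannot settle either possibility. A 12-month reading from someone with no 6-month reading is the most direct evidence the trial could collect on this, and it would also help to impute the missing 6-month value.

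There is a reporting effect too. Section 3.1.3 lists the withdrawal rate and reason as a primary safety endpoint, and the rule counts missed visits in that rate.

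**Working it through.** **1. Does any section reopen follow-up?**

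- 4.7.3: analysis handling only.
- 8.4.4: for pregnancy withdrawals, uses data collected up to the date of withdrawal. It does not address 9.4 cases.
- 5.4.3, visit window table: Visit 5 is timed from a scheduler call in both arms and does not require attendance at Visit 3.
- 5.4.5: the final evaluation is placed 12 months after enrollment.
- 6.2: imputation, with no provision for later measurement.

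No section invites a 9.4 withdrawal back, and nothing in the visit schedule makes Visit 5 depend on Visit 3.

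**2. The plan's own power figures (6.1).** Inputs: 264 analysed, 132 per arm; differences 6.3 and 4.0 mmHg; SDs 13.6 and 9.7 mmHg; two-sided 0.025 each (z = 2.241). Normal approximation: power = Φ(δ / (σ√(2/n)) − z).

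- Systolic: 6.3 / (13.6 × √(2/132)) = 3.763; Φ(3.763 − 2.241) = 0.936, against 0.94 stated.
- Diastolic: 4.0 / (9.7 × √(2/132)) = 3.350; Φ(3.350 − 2.241) = 0.866, against 0.87 stated.

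Both reproduce. They concern the 6-month comparison. The documents give no 12-month effect, SD, retention or power.

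**3. How many are affected.** 340 × 0.15 = 51, leaving 340 − 51 = 289. This is an upper limit, because dropout also includes voluntary withdrawal, pregnancy, adverse events and new ineligibility (2.5.4, 4.7.2, 8.4.4), and the documents do not split dropout by cause.

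**4. What could be gained.** The share r of the 51 who would attend at 12 months is not in the documents, so a range of 10% to 50% is assumed. Further assumptions: the 6-month effects and SDs hold at 12 months, arms are equal, nobody is lost between months 6 and 12, and only observed values are counted.

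| r | Outcomes gained (51 × r) | N at 12 months | Systolic power | Diastolic power |
|---|---|---|---|---|
| 0 (current rule) | 0 | 289 | 0.955 | 0.897 |
| 10% | 5.1 | 294.1 | 0.958 | 0.902 |
| 25% | 12.75 | 301.8 | 0.963 | 0.910 |
| 50% | 25.5 | 314.5 | 0.969 | 0.921 |

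So about 5 to 26 outcomes are gained, and diastolic power rises by 0.5 to 2.4 points. At the top of the range the standard error falls by about 4% (√(289/314.5) = 0.959).

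**5. Scale of possible bias (illustrative).** Suppose all 15% are non-returners, equally in both arms, and their true 12-month treatment effect differs from that of attenders by d. An analysis that in effect carries the attenders' result over to everyone is then wrong by 0.15 × d: 0.15 × 2 = 0.3 mmHg for d = 2, and 0.15 × 5 = 0.75 mmHg for d = 5. The values of d are assumptions. Unequal non-return between arms could give a different figure.

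**The case against.** Several points on the other side stand.

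- **The rule is not triggered by one missed appointment.** A late attender who responds to the calls or letter is not withdrawn. A reader might infer from 9.4 that anyone who misses the visit is removed, or that collected data are thrown away. Neither is supported: the rule follows repeated contact, and the trial fails to seek a value rather than discarding one.
- **The main test is not at stake.** The Study Summary and 6.2 put the primary comparison at 6 months, and the power in 6.1 belongs to that test.
- **Imputation need not use baseline alone.** Intervention participants may have reported home pressures during coaching calls (5.4.2), and healthcare contacts are counted in usual care (5.3). These differ between arms and do not replace a 12-month research pressure.
- **Reachability is unknown.** The life transitions and missed visits described in 2.1 cut both ways. The exclusion for planned moves (4.3) looks only 6 months ahead, so some non-returners may have left the area by month 12.
- **Larger counts are not supported.** A reader might take 340 − 264 = 76 (22.4%) as the number affected. But 340 × 0.85 = 289, so the 264 in 6.1 does not follow from the stated dropout. It needs reconciling in its own right and is not a rate of non-return.

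The planned intention-to-treat analysis, multiple imputation and sensitivity analyses are a reasonable response to missing data, but they cannot create an observation. The full SAP and study calendar are appendices not available here. They may say more about handling missing 12-month data, but an analysis plan cannot recover visits that were never sought.

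**Conclusion.** The point holds as a weakness in follow-up that is cheap to correct. Section 9.4 ends study participation for consenting, still-eligible people who did not return at month 6, while 12-month blood pressure remains a stated outcome. That Visits 5 and 6 are not offered is an inference from withdrawal from the study together with the silence of 4.7.3. No sentence says so outright, which is a further reason to amend the text.

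At most 51 of 340 are affected at 15% dropout. If 10% to 50% of them would attend, about 5 to 26 outcomes are obtainable, with little gain in precision. The main benefit is that the maintenance result would depend less on untestable assumptions. The documents do not show that the 12-month result will be biased. They show that, for this group, the trial gives up its most direct means of checking. The change should be made, but the primary 6-month analysis does not depend on it.

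**What to change.** In 9.4, replace withdrawal with wording such as: *The 6-month visit is recorded as missed; unless the participant withdraws consent or is withdrawn under another section of this protocol, he or she remains in the study and is contacted for the 12-month visits (Visits 5 and 6).* The second exception is needed so that the sentence does not conflict with the withdrawal rules in 2.5.4, 4.7.2 and 8.4.4, which this point leaves as they are.

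In 6.2 and the SAP, state that 12-month values obtained this way enter the 12-month analysis and serve as auxiliary data when 6-month values are imputed. Report 12-month retention by arm, and count missed visits separately from withdrawals for 3.1.3.

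The cost is a one-sentence amendment, a few scheduling contacts per person, and the visits themselves. Section 4.6.6 sets payments of $30 for Visit 5 and $20 for Visit 6. At $50 each, 5 to 26 attenders would cost $250 to $1,300, plus staff time that the documents do not price. No new procedure is needed.
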